#### **10.7 Determination of Sample Size**

Assumptions for sample size calculation are based on the studies of Holtmann et al. and Talley et al. from which a standard deviation of 7 can be assumed for the change of the LD questionnaire.

For the NI margin following assumptions were made:

- In the Holtmann study a difference to placebo 2 (95% CI: 0.03-3.97) in the LDQ was reported.
- In the Ang publication (2011) a difference of 10-15% to placebo is regarded as clinically relevant
- NI-margin needs to be lower than 2. A difference of 15% results in 1.74. Therefore, a NI margin of 1.75 is chosen.

---

Assuming a NI margin of 1.75 and standard deviation of 7 for the change in the LDQ severity score, 253 subjects per treatment arm are required to conclude non-inferiority between the 2 treatment groups with a power of 80% at  $\alpha$ -level of 2.5% single sided. Adding a 10% drop-out rate the total sample size would be 564 subjects (N= 282 per arm).

---

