$\Delta_A$  = Mean change in LDQ score from baseline for Active Control group

Non inferiority will be achieved using the lower bound of the 95% confidence interval of the difference between the Test groups and Active Control group. If the lower bound of the 95% confidence interval of the difference between the Test groups and Active Control group is greater than 1.75 (NI-margin), Test group will be declared non-inferior to Active Control group, and the study will be considered a success.

The above analysis will be performed for both the per protocol and the full analysis set. The analysis for the per-protocol set will be regarded as primary.

For the primary PP analysis, the major protocol deviations/violations will be determined before DB lock.

All data points as results of major deviations/violations will be excluded.

Subjects who have taken the rescue medication marked as minor protocol deviation will be included in Per Protocol sample. All data points will be disregarded and considered as missing after the use of rescue medication.

Resulting missing values will be replaced using MI (like a hypothetical strategy in the estimand framework). Replacing missing values by MI will also be done as part of FAS analysis that otherwise includes all observed.

The data will be separated into two subsets based on the treatment groups which will ensure that the imputation process accounts for potential difference between these groups. Complete dataset will be generated using PROC MI and recombine the data set for subsequent analysis. The number of imputed data set should be sufficient to ensure reliable result. PROC MIANALYZE will be used to combine the results of complete dataset results.

The following sample SAS code pertains to the imputation:

```
/* Step 1: Separate data into two subsets based on treatments and Perform Multiple Imputation separately for each group */
```

```
PROC MI DATA=data OUT=imputed_data NIIMPUTE=X (usually considered 5 for data values missing up to 20%) SEED=XXXXXX;
```

```
Class Site;
```

```
VAR var 1 var 2 var3;
```

```
MONOTONE/FCS REG;
```

```
Run;
```

```
/* Use Monotone or FCS regression imputation based on missing values pattern*/
```

```
/* Step 2:
```

```
Re-combine the imputed dataset for each group and Analyze the imputed dataset */
```

```
PROC MIXED DATA=combined;
```

```
CLASS treatment site;
```

```
MODEL chg = base treatment site/SOLUTION;
```

```
LSMEANS treatment/ STDERR PDIFF CL ALPHA=0.05;
```

```

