    BY _imputation_ ; /* perform analysis for each imputed dataset */  
    ODS OUTPUT DIFFS = diffs LSMEANS = lsmeans; /*Use the ODS Output tables required  
as per need*/;  
run;  
/* Step 3:  
Pooled the result from multiple imputation */  
ODS OOUTPUT PARAMETERESTIMATES=estimate; /*use the ODS Output tables required  
as per need*/  
PROC MIANALYZE DATA=lsmeans/diffs;  
/* If any By variable is required, use BY option*/  
    MODELEFFECTS estimate;  
    STDERR StdErr;  
Run;
```

In order to test robustness of results following analyses will be performed:

- Leeds Dyspepsia Questionnaire (LDQ) severity score will be analyzed using mixed model repeated measure (MMRM) model for FAS population. No missing values will be imputed for the analysis.
- Leeds Dyspepsia Questionnaire (LDQ) severity score will be analyzed using mixed model repeated measure (MMRM) model for PP population where, missing values will be imputed for the data points not excluded due to deviation will be replaced using MI.
- Leeds Dyspepsia Questionnaire (LDQ) severity score will be analyzed using ANCOVA model for PP population that includes subjects who complete all visits of study as per protocol.

The following sample SAS code pertains to the MMRM analysis:

```
PROC MIXED DATA=data METHOD=REML;  
    CLASS Treatment Site Subject Visit;  
    MODEL aval = base treatment site visit treatment*visit /SOLUTION DDFM=kr;  
    REPEATED Visit/ SUBJECT=Subject TYPE=un; /* If UN is not convergence, follow the  
sequence as TOEP, AR(1) and CS */  
    LSMEANS Treatment*Visit /CL DIFF;  
RUN;
```

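### No listed robustness analysis shows how much worse the test arm's missing week-8 LDQ values could be before non-inferiority fails

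*SAP*

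**What the plan says.** SAP 4.2.1 makes the per-protocol (PP) analysis of change in LDQ at week 8 primary. Subjects whose rescue use counts as a minor deviation stay in the PP sample, but "All data points will be disregarded and considered as missing after the use of rescue medication". The gaps are filled by multiple imputation (MI), by regression, run separately in each arm; the SAP likens this to a hypothetical strategy. The full analysis (FA) set also uses MI for missing values but appears otherwise to keep everything observed, including scores after rescue.

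The SAP then states: "In order to test robustness of results following analyses will be performed". The three analyses are:

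- a mixed model for repeated measures (MMRM) on the FA set without imputation;
- an MMRM on the PP set with MI;
- an "ANCOVA model for PP population that includes subjects who complete all visits of study as per protocol".

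The LDQ tables listed in SAP 9.3.1 (10.1.2.1.1.5 to .7 and 10.1.2.1.2.5 to .6) match these analyses and the MI runs. Neither they, the sample code nor the change log in SAP 7.1 contains a delta-adjusted, tipping-point, reference-based or other analysis that departs from missing at random.

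Two places promise more on rescue. The secondary efficacy text in Protocol 10.2 says its impact will be examined by suitable methods, such as imputation, depending on how many subjects need it, and by subgroup. The SAP's other-analysis text, after 4.3, defers the strategy until after the final blind data review. Neither fixes a method, and neither covers withdrawals.

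**The concern.** The primary MI and both MMRMs predict a missing week-8 score from subjects in the same arm with similar observed data. The completers analysis relies on those who finish to stand for those who do not. If test-arm subjects with missing values truly did worse than such predictions, and control subjects did not, the estimate would be biased towards non-inferiority. No listed analysis varies that assumption.

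The question is a real one in this trial. Rescue is for persistent symptoms and may start only after visit 3 (Protocol 4.2 and 7.8). The only later LDQ is at week 8 (Protocol 8.6), so in the PP analysis the value discarded after rescue is the primary endpoint itself. The trial is open-label, and the investigator who confirms rescue knows the arm. Lack of efficacy is also a listed reason for withdrawal (Protocol 6). A departure in one arm only therefore cannot be excluded.

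**Working it through.** **Inputs from Protocol 10.7.** Margin and SD: "Assuming a NI margin of 1.75 and standard deviation of 7 for the change in the LDQ severity score". The same section gives 253 evaluable per arm, 80% power, a one-sided alpha of 2.5%, and 10% drop-out, hence 282 per arm. No true difference is stated; 0 is assumed.

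**Reproducing the plan's figure.** n = 2 × 7² × (1.96 + 0.8416)² / 1.75² = 251.2, so 252 per arm by the normal approximation. The noncentral t version gives 253, with 80.1% power. 253 / 0.90 = 281.1, so 282 per arm and 564 in total. The plan's figures reproduce with a true difference of 0.

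**Assumed, because the documents give no value.** f is the share of week-8 values missing or set to missing in each arm, 5% to 30%. δ is how many points worse the test arm's missing values are than imputed; the control arm's δ is 0 unless stated.

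**Conventions.** Differences are test minus control with a higher LDQ worse, and non-inferiority means that the upper 95% limit is below 1.75. The SE uses SD 7 and observed subjects only, with m = 282 × (1 − f) per arm, rounded down.

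**Tipping point.** SE = 7 × √(2/m), and δ* = (1.75 − D − 1.96 × SE) / f, where D is the observed difference. For f = 10%: m = 253, SE = 7 × √(2/253) = 0.622, half-width = 1.22, and room at D = 0 is 1.75 − 1.22 = 0.53, so δ* = 0.53 / 0.10 = 5.3.

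| f | m | SE | Room at D = 0 | δ* at D = 0 (in SDs) | δ* at D = 0.25 |
|---|---|---|---|---|---|
| 5% | 267 | 0.606 | 0.563 | 11.3 (1.61) | 6.3 |
| 10% | 253 | 0.622 | 0.530 | 5.3 (0.76) | 2.8 |
| 15% | 239 | 0.640 | 0.495 | 3.3 (0.47) | 1.6 |
| 20% | 225 | 0.660 | 0.456 | 2.3 (0.33) | 1.0 |
| 30% | 197 | 0.705 | 0.368 | 1.2 (0.18) | 0.4 |

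**False success at a true difference of 1.75.** The rate for an analysis that assumes missing at random is Φ(f × δ / SE − 1.96).

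| f | δ | f × δ | Formula | Simulated (4,000 trials) |
|---|---|---|---|---|
| 10% | 1.75 | 0.175 | 4.7% | 4.6% |
| 10% | 3.5 | 0.35 | 8.1% | 8.9% |
| 20% | 1.75 | 0.35 | 7.6% | 7.2% |
| 20% | 3.5 | 0.70 | 18.4% | 18.0% |

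With the correct shift applied, the simulated rate in these settings returns to between 2.0% and 2.6%.

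**Both arms departing.** The bias is f_T × δ_T − f_C × δ_C. With equal shares and shifts it is 0, and the rate is Φ(−1.96) = 2.5%. With δ = 3.5 in both arms and SE 0.622, 12% against 10% missing gives a bias of 0.07 and a rate of 3.2%; 15% against 10% gives 0.175 and 4.7%.

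**The case against.** The strongest reply is that missing at random may be a fair assumption here. Rescue cannot start before visit 3, and the LDQ is scored at visit 3, so the symptoms that prompt rescue should largely show in the week-4 score. Missingness that depends on an observed score is what missing at random allows, and the MMRM uses both visits. Rescue is also tied to gastric hypersecretion, not to the total LDQ. A reader might infer that the rescue rule by itself makes the data missing not at random; the documents do not support that. The reply has a limit: the MI sample code gives only placeholder variable names, so use of week 4 in the imputation is not stated. Worsening after week 4, and unblinded decisions, also remain possible.

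A reader might also infer that the listed analyses must agree almost automatically. They need not. The FA set appears to keep observed post-rescue scores while the PP set discards and imputes them, so the two differ in handling as well as in population. But a post-rescue score includes the rescue drug's effect, so it does not test a worse outcome without rescue. For a subject with no week-8 score it adds nothing.

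The promised rescue evaluation counts for something, but it is deferred and has no method. Two further points stand in full: equal departures in both arms cancel, and with little missing data the result is hard to overturn.

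**Conclusion.** The gap is real but limited. The plan pre-specifies no analysis that shows how far the test arm's missing week-8 values could fall short of their imputed values before the conclusion changes. Whether that matters depends on the amount missing. At 5% and an observed difference of 0, a shift of 11.3 points is needed, which is reassuring. At the planned 10% drop-out it is 5.3 points. At 20-30% it is 2.3 to 1.2 points, and less if the observed difference already leans against the test arm.

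False success of about 4.7% to 18% rests on 10-20% missing, a shift of 1.75-3.5 points in the test arm only, and a true difference exactly at the margin. It is not a forecast. A reader might infer a rate of 20% at 20% missing and 3.5 points; that follows only if the SE stays at its value for 253 observed per arm, and 253 is already net of 10% drop-out. Nor do the documents show that departures would fall on the test arm alone.

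The SE here is itself approximate. Baseline adjustment, or use of week-4 data in the imputation, would tend to reduce it; PP exclusions would increase it.

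**What to change.** State first, in the protocol and SAP, which way the difference is taken and the sign of the margin. Both now require the lower confidence limit to exceed 1.75, which leaves the direction unclear, and a tipping point cannot be read against that rule.

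Then, before database lock, add to SAP 4.2.1 a delta-adjusted MI for the PP and FA sets, built on the imputed data sets already planned. Worsen imputed test-arm week-8 LDQ values by 1.75 points, then in steps until non-inferiority is lost, and report the shift at which that happens. Shift rescue-related and withdrawal-related missing values separately. If the FA set keeps post-rescue scores, only values actually missing are shifted there. Keep the completers ANCOVA; nothing requires its removal.

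The cost is a few lines of code and one more table. The adjusted analysis passes less often: at 10% missing and no expected observed difference, the chance of still passing is Φ((1.75 − f × δ) / 0.622 − 1.96), about 72% at a shift of 1.75 and 61% at 3.5. It should therefore be labelled a sensitivity analysis and not a second success criterion.

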### 8.1 Efficacy Measurements

- **Symptoms of dyspepsia using Leeds Dyspepsia Questionnaire (LDQ)**
- LDQ Questionnaire will be completed by the site staff through interview with patient by site staff trained on administration of LDQ to capture the overall symptomatology at screening (visit 1), week 4 (visit 3) and on week 8 (visit 4). The symptoms of dyspepsia are evaluated by measuring its frequency using the LDQ questionnaire which is a fully validated instrument to assess the symptoms of dyspepsia. A dyspepsia questionnaire or Leeds Dyspepsia Questionnaire (LDQ) can identify subjects with dyspepsia by measuring its frequency and therefore will assess the severity via a calculated overall score

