### **4.2.1 Primary Efficacy Analysis**

- **Change in Leeds Dyspepsia Questionnaire (LDQ) Severity Score between baseline and week 8**

A by-participants data listing will be provided for all subject consented subject sample, which contains data information for Leeds Dyspepsia Questionnaire (LDQ) questionnaire from CRF. LDQ severity score and change in LDQ severity score from baseline will also be listed for all participants.

The primary endpoint is the change in the overall severity of functional dyspepsia between baseline and week 8, as measured by the Leeds Dyspepsia Questionnaire (LDQ) severity score.

The values of Leeds Dyspepsia Questionnaire (LDQ) severity score will be derived as per [section 5.3.1](#).

The actual values at baseline and week 8 and values of change from baseline at week 8 will be summarized using the number of non-missing observations (n), mean, standard deviation (SD), median, minimum (Min) and maximum (Max) by Test group and Active Control group.

The primary endpoint Leeds Dyspepsia Questionnaire (LDQ) severity score will be analyzed using analysis of covariance (ANCOVA) model. The model will include change in the LDQ score as dependent variable and treatment groups, site and LDQ baseline value as covariates. Two-sided 95% confidence intervals will be constructed for the Least Square Mean (LS Mean) differences between Test group and Active Control group. Normal approximation will be assumed for the parametric analyses.

The following sample SAS code pertains to the analysis:

```
proc mixed;  
  class TREATMENT SITE;  
  model CHG = BASE TREATMENT SITE/solution;  
  lsmeans TREATMENT/ stderr pdiff cl alpha=0.05;  
  ods output diffs = DIFFS lsmeans = LSMEANS;  
run;  
*CHG: LDQ change from baseline values  
*BASE: LDQ baseline values
```

Non-inferiority of Test group (Itopride Hydrochloride 150 mg extended-release tablets once daily before one of the main meals) compared to Active Control group (Itopride Hydrochloride 50 mg film coated tablets 3 times daily before meals) will be assessed using Full Analysis (FA) and Per Protocol (PP) subject sample for the entire study population.

The non-inferiority margin is set as 1.75 and thus the null and alternative hypothesis will be stated as follows:

Null Hypothesis:

Test group is inferior to active control group

Alternative Hypothesis:

Test group is non-inferior to active control group

Where,

$\Delta_T$  = Mean change in LDQ score from baseline for Test group

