	LDQ	10.1.2.1.1.7	Change in Leeds Dyspepsia Questionnaire (LDQ) Severity Score at week 8 (HDL) for subjects completed the study – Per Protocol Subject Sample		NA	NA

Output Code	Clinical Domain	Output Number	Title	Produced for:		
				Headline Results	SMT	Interim Analysis
	LDQ	10.1.2.1.2.1	Change in Leeds Dyspepsia Questionnaire (LDQ) Severity Score (HDL) – Full Analysis Subject Sample	X	NA	NA
	LDQ	10.1.2.1.2.2	Change in Leeds Dyspepsia Questionnaire (LDQ) Severity Score (by Gender) – Full Analysis Subject Sample	X	NA	NA
	LDQ	10.1.2.1.2.3	Change in Leeds Dyspepsia Questionnaire (LDQ) Severity Score (by Age Group) Full Analysis Subject Sample	X	NA	NA
	LDQ	10.1.2.1.2.4	Change in Leeds Dyspepsia Questionnaire (LDQ) Severity Score (by Geographical Region) – Full Analysis Subject Sample	X	NA	NA

Output Code	Clinical Domain	Output Number	Title	Produced for:		
				Headline Results	SMT	Interim Analysis
	LDQ	10.1.2.1.2.5	Change in Leeds Dyspepsia Questionnaire (LDQ) Severity Score (HDL) at week 8 with Multiple Imputation – Full Analysis Subject Sample			
	LDQ	10.1.2.1.2.6	Change in Leeds Dyspepsia Questionnaire (LDQ) Severity Score (HDL) at week 8 by using MMRM Model – Full Analysis Subject Sample			
	SF-NDI Questionnaire	10.1.2.2.1.1	Summary of Symptoms response assessed by Short Form Nepean Dyspepsia Index (SF-NDI) Questionnaire – Full Analysis Subject Sample	X	NA	NA
	SF-NDI Questionnaire	10.1.2.2.1.2	Summary of Symptoms score assessed by Short Form Nepean Dyspepsia Index (SF-NDI) Questionnaire – Full Analysis Subject Sample	X	NA	NA

Output Code	Clinical Domain	Output Number	Title	Produced for:		
				Headline Results	SMT	Interim Analysis
	SF-NDI Questionnaire	10.1.2.2.2.1	Summary of Functional Dyspepsia Score assessed by Short Form Nepean Dyspepsia Index (SF-NDI) Questionnaire (HDL) – Full Analysis Subject Sample	X	NA	NA
	SF-NDI Questionnaire	10.1.2.2.2.2	Summary of Functional Dyspepsia Score assessed by Short Form Nepean Dyspepsia Index (SF-NDI) Questionnaire (by Gender) – Full Analysis Subject Sample		NA	NA
	SF-NDI Questionnaire	10.1.2.2.2.3	Summary of Functional Dyspepsia Score assessed by Short Form Nepean Dyspepsia Index (SF-NDI) Questionnaire (by Age Group) – Full Analysis Subject Sample		NA	NA

Output Code	Clinical Domain	Output Number	Title	Produced for:		
				Headline Results	SMT	Interim Analysis

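### The MMRM robustness model forces one baseline LDQ slope on weeks 4 and 8; a `base*visit` term would remove a small, conditional bias at almost no cost

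*SAP*

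**What the plan says.** SAP 4.2.1 lists three analyses to test robustness. The first is a "mixed model repeated measure (MMRM) model for FAS population. No missing values will be imputed for the analysis", so it uses the full analysis sample. The second is an MMRM in the per-protocol sample after multiple imputation (MI), and the third an ANCOVA in per-protocol completers. One code block serves the MMRM: "MODEL aval = base treatment site visit treatment*visit /SOLUTION DDFM=kr", with covariance "REPEATED Visit/ SUBJECT=Subject TYPE=un". Nothing else in either document adds a baseline-by-visit term.

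The ANCOVA is coded as "model CHG = BASE TREATMENT SITE/solution" and, for the primary endpoint, is applied to the week 8 change alone. Protocol 8.1 schedules the LDQ at "screening (visit 1), week 4 (visit 3) and on week 8 (visit 4"), so the MMRM has two post-baseline visits.

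Success is judged on the ANCOVA, with the per-protocol sample regarded as primary. The SAP also says: "Replacing missing values by MI will also be done as part of FAS analysis that otherwise includes all observed". SAP 9.3.1 lists that output as Table 10.1.2.1.2.5, "Severity Score (HDL) at week 8 with Multiple Imputation – Full Analysis Subject Sample".

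**The concern.** With `base` as a main effect only, a single coefficient must describe how baseline predicts both week 4 and week 8. The LDQ baseline is taken at screening, up to 14 days before Day 1 (Protocol 8.6), so week 8 lies much further from it than week 4. A flatter slope at week 8 is plausible, and the documents give no reason to assume that the slopes are equal.

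If they differ, the common slope is too steep at week 8. For a subject missing at week 8, the model carries that error into the implied prediction, and the week 4 residual pushes it further the same way. If severe subjects leave one arm more than the other, the errors do not cancel between arms. Even with no missing data the MMRM contrast need not match the ANCOVA contrast. A disagreement between them could then reflect the slope restriction rather than missing data, which weakens the check.

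**Working it through.** **The plan's own figure.** With margin 1.75, SD 7, one-sided 2.5% and power 80%: n = 2(1.960 + 0.842)² × 7²/1.75² = 251.2, so 252 per arm. The noncentral t version first reaches 80% at 253 (80.14%). Then 253/0.9 = 281.1, so 282 per arm and 564 in total, as stated. None of this depends on the MMRM.

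**Inputs not in the documents (assumed).** Baseline SD 6; residual SDs 6 (week 4) and 6.5 (week 8); residual correlation 0.5, so residual covariance 0.5 × 6 × 6.5 = 19.5; true difference 0; site omitted. Slope pairs b4/b8 are 0.5/0.4 and 0.6/0.3.

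**Large-sample bias when drop-out depends on baseline.** Let b* be the fitted common slope and ρ* the fitted regression of the week 8 residual on the week 4 residual.

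- b* = (w4·b4 + w8·b8)/(w4 + w8), with w4 = 42.25 − 19.5 = 22.75 and w8 = 36 − 19.5 = 16.5.
- ρ* = [19.5 + 36(b4 − b*)(b8 − b*)] / [36 + 36(b4 − b*)²].
- Slope excess at week 8: k = (b* − b8) + ρ*(b4 − b*).
- In each arm, d = mean baseline of all subjects minus mean baseline of those observed at week 8 = p/(1 − p) × (mean baseline excess of the missing), where p is the fraction missing.
- Bias of the week 8 difference = k × (d_test − d_control).

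The two conditions follow. Equal slopes give k = 0. Equal dependence in both arms gives d_test = d_control.

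**Slope excess.**

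| b4/b8 | b* | ρ* | k |
|---|---|---|---|
| 0.5/0.4 | (11.375 + 6.6)/39.25 = 0.458 | 0.538 | 0.058 + 0.538 × 0.042 = 0.081 |
| 0.6/0.3 | (13.65 + 4.95)/39.25 = 0.474 | 0.512 | 0.174 + 0.512 × 0.126 = 0.238 |

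**Drop-out.** The model is logistic in a normal baseline; the mean excess of the missing is by numerical integration.

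- Log-odds rising 0.5 per baseline SD, 10% missing in that arm: mean excess 2.64, d = (0.10/0.90) × 2.64 = 0.29.
- Log-odds rising 1.0 per SD, 13.4% missing in that arm (about 12% overall with 10% in the other): mean excess 4.63, d = (0.134/0.866) × 4.63 = 0.72.

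**Bias, in LDQ points.**

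| Pattern | 0.5/0.4 | 0.6/0.3 |
|---|---|---|
| One arm, d = 0.29 | 0.02 | 0.07 |
| One arm, d = 0.72 | 0.06 | 0.17 |
| Opposite directions, difference in d = 1.43 | 0.12 | 0.34 |
| Same in both arms | 0 | 0 |

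Simulation with the same inputs and about 11-12% missing gave shifts against the `base*visit` model of 0.06 and 0.16 (one arm) and 0.11 and 0.34 (opposite), so formula and simulation agree. A second set of assumptions (residual SDs 5.5 and 6, correlation 0.6, 10% drop-out, week 4 slope 0.6, week 8 slope 0.5 to 0.3), with drop-out driven by baseline or week 4 score, gave 0.03-0.16 and 0.07-0.30. In that set the model with the term stayed within about 0.02 of zero in every setting. The sign reverses if the dependence reverses.

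**Precision.** With complete data the SE ratio is √[1 + 36(b* − b8)²/42.25]: 1.001 for 0.5/0.4 and 1.013 for 0.6/0.3. With drop-out, simulated inflation was nil for equal slopes and at most 3.3% for gaps up to 0.3.

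**Departure from ANCOVA with nothing missing.** The two contrasts differ by about (b* − b8) times the chance baseline imbalance, whose SD is 6√(2/282) = 0.505. That gives SDs of 0.058 × 0.505 = 0.03 and 0.174 × 0.505 = 0.09 points.

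**The case against.** The strongest reply is that nothing in the trial's decision depends on this model. The success rule is applied to the ANCOVA, which has its own week 8 slope, and the MMRM has no success criterion. That stands.

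The full-analysis result also does not rest on the MMRM alone. It is the only full-analysis item among the three bullets, but a full-analysis MI ANCOVA is planned as well. The variable list in its imputation code is a placeholder, yet nothing in that code or in the ANCOVA ties the two visits to one slope. A reader might infer that the trial has no unrestricted full-analysis check for missing data; the documents do not support that.

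The full-analysis MMRM also differs from the per-protocol primary in sample and in handling of data after rescue. A disagreement between those two could not be put down to missing data even with the extra term. The gain is in comparing the MMRM with the full-analysis ANCOVA tables, and in the per-protocol MMRM. In the latter the gaps are imputed first, so the drop-out mechanism largely does not operate, but the complete-data departure remains. Exact agreement with ANCOVA would also need `site*visit`.

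Finally, the sizes rest on assumptions. The assumed inputs imply a week 8 change SD of √(0.6² × 36 + 42.25) = 7.4 or √(0.7² × 36 + 42.25) = 7.7, somewhat above the protocol's 7. The documents do not show that the slopes differ.

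**Conclusion.** The term is missing, and the restriction can matter, but only under two joint conditions: slopes that differ by visit, and drop-out that depends on severity differently by arm. It would be wrong to infer that missing-at-random drop-out by itself biases the difference, since the same dependence in both arms gave none. It would equally be wrong to say that the model is always less precise, since with equal slopes nothing is lost.

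Under the assumed inputs, with about 10-12% missing and slope gaps of 0.1 to 0.3, the shift is roughly 0.02-0.16 points for dependence in one arm (1% to 9% of the 1.75 margin) and 0.1-0.35 for opposite dependence (6% to 20%). The SE rises by up to about 3%. A slope pair such as 0.7/0.2, or heavier drop-out, gives larger figures, but these are extreme cases. This is a minor specification point on a supportive analysis. The primary per-protocol ANCOVA, the success decision and the sample size stand as they are.

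**What to change.** Before database lock, append `base*visit` to the fixed effects in the MMRM MODEL statement, after `treatment*visit`, for Table 10.1.2.1.2.6 (full analysis sample) and Table 10.1.2.1.1.6 (per-protocol sample with MI). The covariance structure and the treatment-by-visit LS means can stay as coded. With two post-baseline visits the cost is one degree of freedom, with no new data and no change to the sample size. If the true slopes are equal, the loss of precision is negligible (SE at most about 1% larger in simulation).
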